### 8.7.3. Compliance

Descriptive analyses will be provided on outpatients from the ITT population for the following endpoints:

- Presence of fexinidazole and/or its main metabolites in the blood sample collected on Day 11 and/or at any unscheduled visit between Day 1 and the end-of-treatment (EoT) visit (*note: this endpoint will be analyzed by [REDACTED]*)
- Patients who had tablets left over at the end of treatment (i.e. number of tablets returned on day 11  $>$  0) (yes/no)
- Number of tablets left over at the end of treatment (i.e. number of tablets returned on day 11) (0, 1, 2, ...)
- Patients’ responses to the questionnaire at the compliance interview on Day 11: Questions 5, 5.1, 5.2, 5.3 and 5.4.

Descriptive analyses of other endpoints listed in [Section 6.2.2](#) will be provided by cohorts, by subgroups and overall on the ITT.

Patients for whom the number of tablets taken is different from 24 (14 for children  $<$ 35 kg) or number of treatment day is different from 10 or number of tablets remaining is different from 0 or number of

re-administered tablets is different from 0 or had treatment discontinuation (permanent or temporary) will be listed with all the information concerning their treatment.

The following analysis defined in Section 9.6.2 of the protocol will be provided by [REDACTED]: *“the number and percentage of patients in whom the presence of fexinidazole or its main metabolites was detected in the blood sample collected on D11 will be presented, as well as the success rate in this sub-group of patients and in the subgroup of patients in whom no trace of fexinidazole or its main metabolites was detected. The distribution of the frequency of the number of tablets remaining at the end of the treatment period will be presented, and the relationship between the success rate and the number of tablets remaining will be determined using a logistic regression or a sub-group analysis. The distribution of the frequencies of responses from patients during the compliance interview will be presented. The information provided by the PK analyses, the number of tablets remaining and the questionnaire will be combined to define perfect compliance and noncompliance. Perfect compliance corresponds to a patient in whom fexinidazole is detected in the blood, who has no remaining tablets and whose report on full compliance with treatment seems unquestionable. The success rate in patients with perfect compliance will be compared to that in non-compliant patients”.*

#### 8.7.4. Feasibility

The secondary analyses concerning the feasibility of patient self-management of treatment intake under recommended conditions will be performed on outpatients from the ITT population. The endpoints analysed will be those defined in [Section 6.2.3](#). For each of the endpoints, the proportion of patients will be presented with the 95% CI.

#### 8.7.5. Packaging

Descriptive results of the questionnaires completed at D0 and D11 by the patients and/or caregivers will be presented on an outpatient and/or caregivers basis (sub-group of outpatients from the ITT population).

#### 8.7.6. PK

The statistical analysis of the pharmacokinetic data will be performed by [REDACTED] and is not covered in the current statistical analysis plan. A separate statistical analysis plan will be prepared by [REDACTED] for these analyses. Cf. protocol, Section 9.6.5 for further details.

### 8.8. Safety analysis

Safety analyses will be performed on the mITT.

#### 8.8.1. Secondary endpoints for assessment of safety

Analysis of “occurrence of grade  $\geq 3$  AEs” and “occurrence of any SAE” is described below in [Section 8.8.2](#).

A descriptive analysis will be provided by cohorts, subgroups and overall for the following endpoint: “number of patients who discontinued treatment or were hospitalized for reasons related to safety, including overdose”.

#### 8.8.2. Adverse events

Analysis of adverse events will be based on the concept of treatment-emergent adverse events (TEAE) (cf. definition in [Section 6.3.1](#)).

An overall summary of TEAEs occurring during the 18 months follow-up period (i.e. from first drug intake up-to end of follow-up) will be presented by cohorts, subgroups and overall. The following information will be tabulated (the number, percentage of patient and 95% CI):

- At least one TEAE
- At least one TEAE leading to treatment discontinuation (i.e. permanent or temporary)
- At least one TEAE leading to permanent treatment discontinuation
- At least one mild/moderate TEAE (grade 1, grade 2, mild or moderate)
- At least one severe TEAE (grade 3, grade 4, grade 5 or severe)
- At least one drug-related TEAE
- At least one serious TEAE
- At least one serious TEAE leading to treatment discontinuation (i.e. permanent or temporary)
- At least one serious TEAE leading to permanent treatment discontinuation
- At least one serious drug-related TEAE

For the following descriptions the number and percentage of patients and also the number of occurrences of TEAE will be presented by cohorts, subgroups and overall, and by MedDRA SOC and PT:

- TEAE
- Drug-related TEAE
- Serious TEAE
- Serious drug-related TEAE

All AEs and SAEs will be listed. In addition, TEAE leading to permanent or temporary treatment discontinuation and Drug-related TEAE which occurred during the treatment period (i.e. between the first study-drug intake (included) and the last study-drug intake (included)) will be listed (cf. [Section 9.1](#)).

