2.2.2. Secondary Endpoints - Safety

The secondary endpoints for the assessment of the safety of fexinidazole will be:

- Occurrence of grade ≥ 3 adverse events (AEs), including laboratory and haematological abnormalities (if considered clinically significant), between the first intake of fexinidazole and the end of the observation period* or the follow-up period (18 months) for non-serious AEs assessed as related to fexinidazole. AE severity will be graded according to the National Cancer Institute (NCI) Common Toxicity Criteria for AEs (CTCAE), Version 4.03 (12) and, for certain laboratory parameters, modified CTCAE will be used.
- Occurrence of any serious adverse event (SAE) between the first intake of fexinidazole and the end of the follow-up period (18 months).
- Number of patients who discontinued treatment or were hospitalised during treatment for reasons related to safety, including overdose.
 - *The observation period extends from the first intake of fexinidazole on Day 1 until the end-of-hospitalisation visit (between Day 13 and Day 18) for patients treated in hospital. For out-patients, the observation period extends to the end-of-treatment visit on Day 11.

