### 6.3. Safety endpoints

As defined in the protocol (Section 2.2.2), the secondary endpoints for the assessment of the safety of fexinidazole will be:

- Occurrence of grade  $\geq 3$  adverse events (AEs), including laboratory and haematological abnormalities (if considered clinically significant), between the first intake of fexinidazole and the end of the observation period\* or the follow-up period (18 months) for non-serious AEs assessed as related to fexinidazole.
- Occurrence of any serious adverse event (SAE) between the first intake of fexinidazole and the end of the follow-up period (18 months).
- Number of patients who prematurely discontinued treatment (i.e. prior to Day 10) or were hospitalised for reasons related to safety\*\* (e.g. including overdose).

\* The observation period extends from the first intake of fexinidazole on Day 1 until the end-of hospitalisation visit (between Day 13 and Day 18) for patients treated in hospital. For outpatients, the observation period extends to the end-of-treatment visit on Day 11.

\*\* A patient will be considered as “hospitalised for reasons related to safety” if he/she experienced a SAE during the treatment period and he/she was initially planned to be treated as an outpatient and he/she was hospitalized during the treatment period.

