#### Definition of treatment-emergent AEs:

Treatment-emergent AEs are defined as any AE which occurs on or after the date of the first study-drug administration until the end of the follow-up visit (i.e. 18-month visit).

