## **3. Safety**

### **3.1 Adverse events**

Statistical Table 3.1.1: Overall summary of AEs (mITT)

Statistical Table 3.1.2: TEAE by SOC and PT (mITT)

Statistical Table 3.1.4: Drug-related TEAE by SOC and PT (mITT)

Statistical Table 3.1.5: Serious TEAE by SOC and PT (mITT)

Statistical Table 3.1.7: Serious drug-related TEAE by SOC and PT (mITT)

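### No planned summary table applies the window of the first safety endpoint (grade 3 or higher AEs); the 18-month severe-TEAE row reported for it also counts patients whose only such event is a late SAE

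*SAP*

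**What the plan says.** Protocol 2.2.2 and SAP 6.3 define the first safety endpoint in the same two parts.

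- Grade 3 or higher AEs of any kind count "between the first intake of fexinidazole and the end of the observation period".
- The window is longer for one class only: "or the follow-up period (18 months) for non-serious AEs assessed as related to fexinidazole".

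The observation period runs from the first dose "until the end-of-hospitalisation visit (between Day 13 and Day 18) for patients treated in hospital". The protocol adds: "For out-patients, the observation period extends to the end-of-treatment visit on Day 11".

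SAP 8.8.1 says that the analysis of this endpoint is described in 8.8.2. Section 8.8.2 is built on treatment-emergent AEs, which SAP 6.3.1 defines as any AE "which occurs on or after the date of the first study-drug administration until the end of the follow-up visit", that is, the 18-month visit. Its overall summary is labelled as covering the 18-month follow-up. The one row in it that concerns grade 3 or higher events is "At least one severe TEAE (grade 3, grade 4, grade 5 or severe".

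Protocol 6.8.4 sets what is collected. Non-serious AEs are recorded up to the end-of-hospitalisation visit (in-patients) or Day 11 (out-patients), and after that only if considered related to the drug. SAEs are recorded from consent to 18 months whatever their causality.

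**The concern.** The endpoint and the output assigned to it have different windows. The endpoint stops counting unrelated events, and serious events, at Day 11 or Day 13–18. The row keeps counting SAEs to 18 months. SAP 6.3 presents the endpoint as the protocol defines it, and SAP 11, which has a heading for changes to the AE analysis, mentions no change of window.

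A reader of the study report would therefore take the percentage and confidence interval in the severe-TEAE row for the protocol's first safety endpoint. That figure would combine full AE collection over the treatment period with mainly SAE collection over the following months. It would also overlap with the second safety endpoint (any SAE to 18 months), which already captures the late SAEs.

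**Working it through.** **1. Inputs.** The documents give no expected rate for this endpoint, so there is no plan figure for it to reproduce. Their only sizing figure is 174 patients, for a Wald half-width of 5% at an 87% success rate. It reproduces: 1.96² × 0.87 × 0.13 / 0.05² = 173.8, rounded up to 174. It is used below only to turn percentages into patients.

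**2. Which grade 3 or higher events count where.**

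| Event | Collected (Protocol 6.8.4) | In the endpoint (SAP 6.3) | In the severe-TEAE row (SAP 6.3.1, 8.8.2) |
|---|---|---|---|
| Any AE in the observation period | yes | yes | yes |
| Later, non-serious, related | yes | yes | yes |
| Later, non-serious, unrelated | no | no | no (not collected) |
| Later SAE, related or unrelated | yes | no, read literally | **yes** |

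Only the last line differs. The row therefore equals the endpoint plus the patients whose only grade 3 or higher event is an SAE after the observation period.

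**3. Other planned outputs.** SAP 8.8.2 and 9.1 contain no summary table restricted to the observation period. The nearest output is a listing of drug-related TEAEs between first and last dose. The endpoint could be rebuilt only from the individual AE listings.

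**4. Size.** Let p be the proportion of patients meeting the endpoint and q the proportion of the remaining patients with a late grade 3 or higher SAE. Then

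row = p + (1 − p)q, and excess = (1 − p)q.

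Both p and q are assumptions. The row would show:

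| | q = 0 | q = 1% | q = 2% | q = 5% | q = 10% |
|---|---|---|---|---|---|
| p = 2% | 2.0% | 3.0% | 4.0% | 6.9% | 11.8% |
| p = 5% | 5.0% | 6.0% | 6.9% | 9.8% | 14.5% |
| p = 10% | 10.0% | 10.9% | 11.8% | 14.5% | 19.0% |

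At p = 5% the excess runs from 0.95 × 1% = 0.95 points to 0.95 × 10% = 9.5 points, so the row is 1.2 to 2.9 times the endpoint. The ratio is 1.5 to 5.9 at p = 2% and 1.1 to 1.9 at p = 10%, over the same non-zero values of q.

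For example, take p = 5% and q = 5% with 174 patients. The endpoint is about 9 patients (exact 95% CI 2.4% to 9.6%). The row is about 17 patients (5.8% to 15.2%). About half of the patients in the row would then be there because of a late SAE alone.

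**The case against.** The strongest reply is that the row nearly is the endpoint. Late non-serious AEs are collected only if related, which is the endpoint's own rule, so the row adds nothing except late SAEs. It is a superset of the endpoint and coincides with it if no patient has a late SAE as the only grade 3 or higher event. The SAP table is openly labelled as covering 18 months, any excess errs towards counting more harm, and the endpoint is descriptive and secondary in a single-arm study. All of this stands, and it limits the consequence. It does not supply the stated endpoint, because the plan cannot know in advance that there will be no such patients.

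A reader might infer more than the documents support:

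- **That severe AEs of every kind are counted for 18 months instead of 11 to 18 days.** The collection rules in Protocol 6.8.4 exclude this.
- **That only unrelated SAEs are added.** Read literally, related late SAEs are added too, because the endpoint's extension covers non-serious events only.
- **That the endpoint should be cut off at the end of the observation period.** It also includes related non-serious events to 18 months: "end of the observation period* or the follow-up period (18 months) for non-serious AEs assessed as related to fexinidazole".
- **That a definite number of patients will be added.** The documents give no SAE rate, and any honest range includes zero.
- **That the lack of a table by organ class and term is part of the error.** Such tables are planned for all, drug-related, serious and serious drug-related TEAEs (for example "Statistical Table 3.1.5: Serious TEAE by SOC and PT (mITT"), but none for grade 3 or higher events. Protocol 9.6.1 asks for an organ-class description of SAEs and of AEs leading to discontinuation, and no passage requires one for grade 3 or higher events. The full AE and SAE listings, SAE narratives and laboratory shift tables by CTCAE grade also carry part of this information.

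**Conclusion.** The point holds: as written, no planned summary table gives the first safety endpoint. The row that stands in for it answers a different question, and the SAP does not say so.

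The difference is confined to patients whose only grade 3 or higher event is an SAE after the observation period. Its size is (1 − p)q. It is zero if there are no such patients and, at an assumed p of 5% with q between 1% and 10%, about 1 to 10 percentage points. The mismatch of windows follows from the text alone; the size rests wholly on assumed rates. The primary analysis is unaffected and no data are lost. This is worth correcting because a named secondary endpoint would otherwise be reported with the wrong proportion and interval whenever such patients exist.

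**What to change.** Add to SAP 8.8.2, and to the table list in 9.1, one row for the mITT population with n, % and exact 95% CI, overall and by cohort. It should count patients with either of the following:

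- a grade 3 or higher AE with onset in the observation period; or
- a related non-serious grade 3 or higher AE with onset up to 18 months.

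Report this row as the first safety endpoint. Keep the 18-month severe-TEAE row as supplementary and label it so. Treat events graded only as severe (those outside the CTCAE, Protocol 6.8.6) as the existing row does. Also state which end of the observation period applies to out-patients who are admitted during treatment: SAP 5 keeps them in the out-patient cohort, while Protocol 6.5 follows them as in-patients. If the row is added after database lock, record it in SAP 11. It completes a pre-specified endpoint and does not change one.

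A table of these events by organ class and preferred term would be useful but is optional.

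The cost is one additional table row, or one further table if the optional breakdown is included, from onset dates, grades, seriousness and causality already collected.

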#### **8.8.3. Laboratory examination**

For continuous data, a descriptive analysis will be provided for baseline, at each time point and for the changes from baseline at each time point, by cohorts, subgroups and overall.

Changes in blood levels over time will be presented in graphs.

Shift tables between baseline severity (normal value, abnormal not clinically significant, abnormal clinically significant) and severity at each timepoint (i.e. D5, D11, M3, M6, M12, M18) for each laboratory parameters will be provided by cohorts, subgroups and overall.

Scattergrams between baseline value and value at each timepoint (i.e. D5, D11, M3, M6, M12, M18), for each laboratory parameters will be provided by cohorts, subgroups and overall.

Proportions of patients by category corresponding to the size of the increase in relation to the ULN for liver function tests (i.e. ALT, AST, total bilirubin and alkaline phosphatase) will be described (< 1 ULN, 1–2 ULN, 2–3 ULN etc.) by cohorts, subgroups and overall.

A listing of patients with clinically significant abnormalities in laboratory parameters will be provided (cf. [Section 9.1](#)).

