6.7.2. Procedures at Follow-up Visits at 3, 6, 12 and 18 months

Whether the patient is being treated in hospital or as an out-patient, the following procedures will be performed at Follow-up Visits at 3, 6, 12 and 18 months:

- Collection of blood and/or lymph samples for testing for parasites;
- Collection of CSF for WBC and detection of trypanosomes. At the 3-month follow-up visit, lumbar puncture will be performed only if indicated by the patient's clinical status;
- Collection of signs and symptoms of HAT, if any;
- Karnofsky Performance Status;
- Vital signs: body temperature, blood pressure, heart rate and respiratory rate;
- Physical and neurological examinations;
- Urine pregnancy test for women of child-bearing potential, only at 3-month and 6-month visits;
- Collection of SAEs
- Collection of non-serious AEs assessed as related to fexinidazole;
- Laboratory safety assessments (see Appendix 3 Laboratory Tests; p 75) when possible, samples will be collected in the morning from patients in the fasting state:
 - Haemoglobin;
 - Haematology: WBC, platelet count;

Confidential Page 38 of 83

o Biochemistry: albumin, ALP, ALT, AST, BUN, chloride, creatinine, glucose, potassium, sodium, calcium, total bilirubin, bicarbonates and total protein.

Laboratory safety assessments will be performed at the 12-month and 18-month visits only if indicated by the patient's clinical status.

In the event that a patient moves house or is travelling away from home during the follow-up period, the Investigator accompanied by any necessary study team members may travel to the patient's new place of residence in order to perform one or more follow-up visits.

The patient could also attend one or more follow-up visits in another investigational centre or in a satellite centre. The patient would then be managed by the Investigator in the other investigational centre or by the Coordinating Investigator at the PNLTHA.

The site investigator and his/her study team can also travel to the satellite site to monitor the patient.

In that case, the Investigator in the patient's original investigational centre should inform the Coordinating Investigator and the person in charge of monitoring that a visit is planned to take place in a different investigational centre.

Data collected at such visits will then be sent, within a reasonable timeframe after the visit, to the patient's original investigational centre in order to be recorded in the CRF.

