	Type of test	Specific test	Number of samples	Quantity per sample (approx.)	Total volume per visit
		Woo/CTC	1	100 µL	
	Parasitology	Thin/thick blood smear	1	≤ 300 µL	≤ 400 µL
		mAECT (±BC)	1	5 mL	5 mL
Blood		Haemoglobin	1	20 µL	
Біооц	Haematology (M3 and M6)	WBC	20 µL	170 ul	
		Platelet count	1	10 µL	170 μL (capillary
		Differential WBC	1	20 µL	blood ¹⁾
	Biochemistry (M3 and M6)	14 parameters	1	100 µL	
Lymph	Parasitology	If lymph nodes detectable			
CSF	Parasitology	Modified Single Centrifugation	1	4 mL	4 mL
Urine	Pregnancy (M3 and M6)		1	5 mL	5 mL

Quantity of blood required for PK analyses

Entire study

	Type of test	Number of samples	Quantity per sample (approx.)	Total volume
Blood	PK	6	2mL	12 mL

All haematological and biochemical analyses can be performed using a single finger-prick with a Tenderlett® device or similar.

Confidential Page 77 of 83

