Appendix 7 - Schedule of Study Events

Table 5 – Schedule of Events - Patients treated in hospital

Protocol-planned procedures and forms to be completed	Screening					Treatm	ent per	iod		In-ho	spital Follo	Follow-up period			
Timepoint →	D-15 to D-1	D1	D2	D3	D4	D5	D6	D7	D8	D9	D10	D11 (EoT)	D12	D13-D18 (EoH)	3 – 6 – 12 – 18 months
Rapid Diagnostic Test or CATT	х														
Detection of parasite in blood and/or lymph	Х											х			Х
Informed consent (before any additional medicines or study-specific procedures)	х														
Lumbar puncture (parasite and white blood cells in CSF)	х														x ¹
Pretreatment of helminthiasis ²	х														
Rapid Diagnostic Test and/or thick blood smear for diagnosis of malaria and, if necessary, treatment ²	х														
Karnofsky Performance Status	х											Х			Х
Inclusion and exclusion criteria	х														
Demographic data	х														
Medical history	х														
Signs and symptoms of HAT	х											х			Х
Vital signs ³	х								X ⁴			х		х	Х
Physical and neurological examinations	х								X ⁴			Х		х	Х
Haematology and biochemistry	х											х			X ⁵
Urine analysis	х											х			
Urine pregnancy test	X (D-1)											х			X (3 and 6 months only)
Triplicate ECG	x (D-1)				X D4 H4	X D4 H23	3					х			
Administration of fexinidazole		Х	Х	Х	Х	Х	Х	Х	Х	х	Х				
Blood sampling for PK analyses (specific patient groups)									X H3.15	Х Н3	X H3 H7.15	X D10H24	X D10H48		
Adverse event (AE) collection	X (if considered related to study participation)	х	х	х	х	х	х	х	х	х	х	х	х	х	X (If reasonable possibility of relation to treatment)
Serious adverse event (SAE) collection from signature of consent form to last study visit	х	Х	х	х	х	х	х	х	х	х	х	х	х	х	х
Collection of concomitant medication	х	Х	Х	Х	х	Х	х	х	х	х	Х	Х	х	Х	

Page 82 of 83

Confidential

¹ At 3 months, only if indicated by patient's clinical status.

² Treatment according to national guidelines.

³ Temperature, blood pressure, heart rate and respiratory frequency.

⁴ Only if indicated by patient's clinical status.

⁵ At 3 and 6 months. At 12 and 18 months only if indicated by patient's clinical status.

Protocol DNDi-FEX-09-HAT Version 3.0 Fexinidazole

Table 6 – Schedule of Events - Patients treated on an out-patient basis

Protocol-planned procedures and forms to be completed ${\sf Timepoint} \ \to $	Screening D-15 to D-1	Dispensing D0	Treatment period										Follow-up period	
			D1	D2	D3	D4	D5	D6	D7	D8	D9	D10	D11 (EoT)	3 – 6 – 12 – 18 months

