Rapid Diagnostic Test or CATT	х													
Detection of parasite in blood and/or lymph	x												Х	х
Informed consent (before any additional medicines or study-specific procedures)	х													
Lumbar puncture (parasite and white blood cells in CSF)	Х													x ¹
Pretreatment of helminthiasis ²	х													
Rapid Diagnostic Test and/or thick blood smear for diagnosis of malaria and, if necessary, treatment ²	х													
Karnofsky Performance Status	х												х	х
Inclusion and exclusion criteria	х													
Demographic data	х													
Medical history	х													
Signs and symptoms of HAT	х												х	Х
Vital signs ³	х												Х	Х
Physical and neurological examinations	х												х	х
Haematology and biochemistry	х												х	X ⁴
Urine analysis	x												Х	
Urine pregnancy test	X (D-1)												х	X (3 and 6 months only)
Triplicate ECG	X (D-1)												х	
IMP dispensing / Discharge from hospital		х												
Administration of fexinidazole			х	х	х	х	х	х	х	х	х	х		
Blood sampling for PK analyses													X D10H24 ⁵	
Assessment of understanding of instructions for treatment (questionnaire)		Х												
Treatment compliance (interview)													Х	
Acceptability of packaging (questionnaire)													Х	
Adverse event (AE) collection	X (if considered related to study participation)												X (interview)	X (If reasonable possibility of relatio to treatment)
Serious adverse event (SAE) collection from signature of consent form to last study visit	•													-
Collection of concomitant medication	х												X (interview)	

¹ At 3 months, only if indicated by patient's clinical status.

² Treatment according to national guidelines.

³ Temperature, blood pressure, heart rate and respiratory frequency.

⁴ Only if indicated by patient's clinical status.

⁵ Additional sampling for PK may be performed between Day 1 and Day 11 if the patient returns to the centre for an unscheduled visit

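### SAP 8.8.3 treats Day 5, M12 and M18 laboratory values as routine timepoints, but the protocol schedules no Day 5 sample and tests at M12 and M18 only on clinical indication, so the late summaries describe a selected subset.

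*SAP*

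**What the plan says.** **SAP.** Section 8.8.3 sets shift tables comparing baseline severity with "severity at each timepoint (i.e. D5, D11, M3, M6, M12, M18" and uses the same list for graphs: "Scattergrams between baseline value and value at each timepoint (i.e. D5, D11, M3, M6, M12, M18". Continuous parameters are summarised "for baseline, at each time point and for the changes from baseline at each time point, by cohorts, subgroups and overall". The section adds that "Changes in blood levels over time will be presented in graphs". It contains no restriction, caveat or denominator rule for particular visits. The liver-function categories, in multiples of the upper limit of normal, name neither visits nor a denominator.

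**Protocol.** Section 6.7.2 states: "Laboratory safety assessments will be performed at the 12-month and 18-month visits only if indicated by the patient's clinical status". Footnote 5 of Table 5 (Appendix 7, hospital patients) agrees: "At 12 and 18 months only if indicated by patient's clinical status". The follow-up sampling table in Appendix 3 labels the blood tests by visit, for example "Biochemistry (M3 and M6", and labels haematology the same way. Section 1.6 gives the aim as additional laboratory data at 3 and 6 months, with a focus on haematological and hepatic function.

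**Day 5.** The only assessment specific to Day 5 in Table 5 is the pre-dose ECG for hospital patients. Table 6 shows no out-patient visit that day. Neither table has haematology or biochemistry on Day 5.

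**The concern.** At Day 11, and at M3 and M6 under Protocol 6.7.2, nearly everyone who attends should be sampled. At M12 and M18 a sample exists only because something about the patient's condition called for it. SAP 8.8.3 nevertheless gives all these visits equal standing. A mean, a change from baseline or a percentage at M12 then describes different patients from those at M6, and a difference between the two may reflect only who was tested.

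This matters because liver and blood findings will be read closely. Protocol 1.4 reports liver-function reactions and transient grade 3 and 4 neutropenia with this drug in Chagas disease. Apparent late abnormalities could be taken for a delayed drug effect, and a genuine late effect could not be separated from selection.

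**Working it through.** **Step 1: the plan's own figures.** The documents attach no number to this point. Their computed design figure is the sample size: 1.96² × 0.87 × 0.13 / 0.05² = 173.79, rounded up to 174. It reproduces and is not affected. It is used below as the size of the mITT set, on which SAP 8.8 bases the safety analyses.

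**Step 2: schedule against analysis (haematology and biochemistry).**

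| Visit | Protocol | SAP 8.8.3 |
|---|---|---|
| Day 5 | not scheduled | listed |
| Day 11 | routine | listed |
| M3, M6 | routine in 6.7.2 and Table 5; conditional for out-patients in Table 6, footnote 4 | listed |
| M12, M18 | on clinical indication only | listed |

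**Step 3: what selection can do to a percentage.** All inputs except 174 are assumptions. Let q be the true share with an abnormal value, unchanged over time. Let t1 be the probability of being tested if abnormal and t0 if not.

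- Number tested = 174 × [q·t1 + (1 − q)·t0]
- Abnormal among those tested = q·t1 / [q·t1 + (1 − q)·t0]
- Abnormal over all mITT patients = q·t1

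For q = 5%, t1 = 50%, t0 = 10%: 174 × (0.025 + 0.095) = 20.9 tested, and 0.025 / 0.120 = 20.8%.

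| q | t1 / t0 | Tested | % of tested | % of 174 |
|---|---|---|---|---|
| 5% | 20% / 20% | 34.8 | 5.0 | 1.0 |
| 5% | 50% / 10% | 20.9 | 20.8 | 2.5 |
| 5% | 80% / 5% | 15.2 | 45.7 | 4.0 |
| 10% | 20% / 20% | 34.8 | 10.0 | 2.0 |
| 10% | 50% / 10% | 24.4 | 35.7 | 5.0 |
| 10% | 80% / 5% | 21.8 | 64.0 | 8.0 |

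With patients tested as denominator, the table is correct if testing ignores the value and too high if testing favours abnormal values. With all 174 as denominator, every row falls below the true rate. The SAP does not say which denominator applies.

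**Step 4: what selection can do to a mean change.** A simulation set the true mean change to zero and tested the 5%, 10% or 30% of patients with the highest indication score. That score had correlation ρ with the laboratory change. The apparent mean change among those tested was:

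- 0 SD at ρ = 0
- 0.35 to 0.62 SD at ρ = 0.3
- 0.69 to 1.23 SD at ρ = 0.6

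**Step 5: related rules that do not agree.**

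- *Out-patients.* Footnote 4 of Table 6 makes all follow-up haematology and biochemistry conditional ("only if indicated by patient's clinical status"), with no exemption for M3 and M6, against Protocol 6.7.2. Table 5 has a footnote 4 with the same wording, attached to Day 8 vital signs and examinations. The footnote may have been carried over, but the documents do not say so.
- *Unscheduled visits.* SAP 7.5 analyses them in the matching time window. SAP 8.11 confines most of their data to listings unless the data review selects them. Under the first rule, more indication-driven values enter the M12 and M18 windows.

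**The case against.** A reader might infer that the late tables and graphs will show spurious deterioration. The documents do not support that.

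- They give neither the number tested late nor how strongly the indication relates to any parameter.
- With an all-mITT denominator, shift-table percentages would be diluted, not inflated.
- Protocol 6.8.3 requires clinically significant laboratory abnormalities to be retested until normal or back to baseline. Some late samples could therefore show recovery.
- The SAP output list (9.1, item 3.2.2) drops the change-over-time figure for biochemistry. On the listed outputs, the curve problem is confined to haematology, although 8.8.3 plans graphs in general.

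The plan also has safeguards. SAP 7.4 reports N and missing counts for continuous variables. The severity shift template in 9.2.11 has a Missing row and column. SAP 9.1 already lists individual laboratory values, including unscheduled visits. Under SAP 6.3, laboratory abnormalities count as adverse events only when investigators report them, so the protocol's safety endpoints do not rest on these tables. M3 and M6 are still reported in full. Finally, SAP section 4 cites protocol version 2.0, whereas the protocol supplied is version 3.0; whether the laboratory schedule differed cannot be checked.

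These points rule out any claim of certain or quantified bias. They do not remove the mismatch. Showing N reveals a small subset but does not make it comparable. The CTCAE shift template has no Missing category, and neither shift template defines its percentage base.

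**Conclusion.** The point holds as a mismatch between analysis and sampling. Followed as written, SAP 8.8.3 produces M12 and M18 means, changes from baseline, shift tables, scattergrams and a haematology time course from patients selected on clinical status. It also lists a Day 5 timepoint for which no sample is scheduled. The late results are not comparable with Day 11, M3 and M6. They may be biased, most plausibly towards apparent worsening, because indication tends to pick out patients with problems.

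The size cannot be fixed from the documents. Under the assumptions above, a true 5% could appear as anything from 1.0% to 45.7%, depending on who is tested and on the denominator. The displays are descriptive, so the primary endpoint and the sample size are unaffected.

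**What to change.** **First reconcile:**

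1. Table 6, footnote 4, with Protocol 6.7.2, on whether out-patient M3 and M6 tests are routine. Until this is settled, the routinely sampled visits are not defined for out-patients.
2. SAP 7.5 with SAP 8.11, on how unscheduled values are used.

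**Then amend SAP 8.8.3, the 3.2.x outputs and template 9.2.11:**

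- Restrict by-visit haematology and biochemistry tables and figures to the routinely scheduled visits: baseline, Day 11, M3 and M6.
- Remove Day 5.
- Show M12, M18 and other indication-driven values in the existing listings, or in a separate display labelled as clinically indicated, with the number tested and the reason for testing.
- Add a worst post-baseline value per patient, so that late abnormalities stay visible.
- Define the denominator of the shift tables and liver-function categories as patients tested, and add a Missing category to the CTCAE template.

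**Cost.** SAP wording and fewer table columns, with no change to data collection. The price is that late values leave the main by-visit tables. SAP section 11 already has a heading for changes after database lock; if the lock has passed, this change should be recorded there.
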